### 7.3 Analysis Visit Windows

Refer to Protocol Section 4.3 for the schedule of assessments.

Study days are calculated from the LTT start date as follows:

- Measurement date – LTT start date + 1, if measurement date  $\geq$  LTT start date
- Measurement date – LTT start date, if measurement date  $<$  LTT start date.

Treatment days are calculated from the study drug start date as follows:

- Measurement date – study drug start date + 1, if measurement date  $\geq$  study drug start date
- Measurement date – study drug date, if measurement date  $<$  study drug start date.

Follow-up days are calculated from the LTT last date as follows:

- Measurement date – LTT last date, if measurement date  $\geq$  LTT last date + 1
- Measurement date – LTT last date – 1, if measurement date  $<$  LTT last date + 1

Evaluation intervals are based on study days in the LTT analysis period and follow-up days in the follow-up analysis period (see Section 7.2). Table 3 presents analysis visit windows.

**Table 3: Analysis Visit Windows**

Analysis Period		Analysis Day				
Analysis Visit	Abbreviation in Listings	Analysis-specified Interval	Target Day			
Pre-LTT	PRELTT	Study Day				
Screening		$\leq -6$ or missing				
Pre-Baseline	Prebaseln	-5 to -1				
Baseline		1				
LT	LT	Study Day				
Week 2		1 to 21				
Week 4		22 to 42				
Week 8		43 to 70				
Week 12		71 to 98				
Week 16		99 to 126				
Week 20		127 to 154				
Week 24		155 to 182				
Week 28		183 to 210				
Week 32		211 to 238				
Week 36		239 to 266				
Week 40		267 to 294				
Week 44		295 to 322				
Week 48		323 to 350				
Week 52		351 to 378				
Extension *	Ext	$\geq 379$				
Follow-up	FU	Follow-up Day				
Follow-up Week 2	FU Week 2	1 to 21				
Follow-up Extension *	FU Ext	$\geq 22$				

\* Denotes an extended visit in the analysis period and is displayed primarily in listings

Note that the baseline analysis visit in [Table 3](#) is independent of the baseline value for a parameter defined in [Section 6.2.5](#). The former is used only in by-subject listings that display visit and in COVID-19 analyses by analysis visit (see [Sections 6.6.2](#) and [6.6.3](#)).

## 7.4 Duplicate Subjects

If the same subject is treated in the study more than once and is assigned more than 1 subject identifier (see [Section 9.2](#)), then the following conventions apply to analyses:

- Pre-treatment derived dates (i.e., OP start/end dates, LTT start date, study drug start date) are derived using data only from the subject identifier corresponding to the first treatment.

- All other derived dates (i.e., LTT end/last date, study drug end/last date, last contact date) are derived using data from all duplicate subject identifiers.
- Baseline characteristics excluding non-study prior medications are assessed using data only from the subject identifier corresponding to the first treatment.
- Protocol deviations, non-study prior medications, exposure, safety, migraine days, and outcomes research endpoints are assessed comprehensively using data from all duplicate subject identifiers.
- Subject disposition during treatment table displays study exit status data from the last duplicate subject identifier.
- Listings of subject disposition, protocol deviations, safety, exposure, migraine days, and outcomes research displays data from all duplicate subject identifiers under the subject identifier corresponding to the first treatment.

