### **eDiary Zavegepant and LTT Exposure**

eDiary zavegepant and LTT exposure is tabulated as continuous or categorical variables for the safety analysis set, and includes the following parameters:

- Time in the OP (weeks), derived as  $(OP\ end\ date - OP\ start\ date + 1)/7$
- Time from LTT start to last contact (weeks), derived as  $(last\ contact\ date - LTT\ start\ date + 1)/7$
- Time in the LTT period (weeks), derived as  $(LT\ end\ date - LT\ start\ date + 1)/7$
- Time in the LTT period (weeks) categories:  $\geq 11$ ,  $\geq 23$ ,  $\geq 51$ . These correspond to using a 1-week lower bound on 3, 6, and 12 months, respectively.
- Time on zavegepant (weeks), derived as  $(study\ drug\ end\ date - study\ drug\ start\ date + 1)/7$
- Time on zavegepant (weeks) categories:  $<12$ ,  $\geq 12$  to  $< 24$ ,  $\geq 24$  to  $< 36$ ,  $\geq 36$  to  $< 48$ ,  $\geq 48$ . These align with subgroups specified in Section 4.3.
- Cumulative zavegepant exposure (sprays), derived by summing number of sprays across records with complete study drug dates
- Cumulative zavegepant exposure (sprays) categories:  $< 20$ ,  $\geq 20$  to  $< 40$ ,  $\geq 40$  to  $< 60$ ,  $\geq 60$  to  $< 80$ ,  $\geq 80$ . These align with subgroups specified in Section 4.3.
- Average zavegepant exposure (sprays per month), derived as (1) cumulative zavegepant exposure (sprays) if time in the LTT period  $< 2$  weeks, or (2)  $4 \times$  cumulative zavegepant exposure/time in the LTT period if time in the LTT period  $\geq 2$  weeks.
- Average zavegepant exposure (sprays per month) categories:  $< 6$ ,  $\geq 6$ . These align with subgroups specified in Section 4.3.
- Number and percentage of subjects who administered  $> 1$  spray on any 1 day
- Number and percentage of subjects who administered  $> 8$  sprays per month in any month
- Exposure categories, defined as the number and percentage of subjects who administered
  - $\geq 1$  spray per month for 1, 2, 3, 4, 5,  $\geq 12$ ,  $\geq 6$ ,  $\geq 3$  and  $\geq 1$  months
  - $\geq 2$  sprays per month for 1, 2, 3, 4, 5,  $\geq 12$ ,  $\geq 6$ ,  $\geq 3$  and  $\geq 1$  months
  - $\geq 3$  sprays per month for 1, 2, 3, 4, 5,  $\geq 12$ ,  $\geq 6$ ,  $\geq 3$  and  $\geq 1$  months

- $\geq 4$  sprays per month for 1, 2, 3, 4, 5,  $\geq 12$ ,  $\geq 6$ ,  $\geq 3$  and  $\geq 1$  months
- $\geq 5$  sprays per month for 1, 2, 3, 4, 5,  $\geq 12$ ,  $\geq 6$ ,  $\geq 3$  and  $\geq 1$  months

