- $\geq 6$  sprays per month for 1, 2, 3, 4, 5,  $\geq 12$ ,  $\geq 6$ ,  $\geq 3$  and  $\geq 1$  months
- $\geq 7$  sprays per month for 1, 2, 3, 4, 5,  $\geq 12$ ,  $\geq 6$ ,  $\geq 3$  and  $\geq 1$  months
- $\geq 8$  sprays per month for 1, 2, 3, 4, 5,  $\geq 12$ ,  $\geq 6$ ,  $\geq 3$  and  $\geq 1$  months.
- Total zavegepant exposure (sprays) summed across all subjects, derived by summing cumulative exposure across all subjects
- Total zavegepant exposure (patient-years), derived by summing (study drug end date – study drug start date + 1)/365.25 across all subjects.

See Section 7.1 for derived dates.

eDiary zavegepant and LTT exposure is also tabulated by subgroup level and overall for the safety analysis set for all subgroups of interest described in Section 4.3.

Months are 4-week (28-day) intervals in the LTT analysis period defined as follows:

- Month 1 ( $\leq 4$  weeks; study days 1 to 28)
- Month 2 ( $> 4$  to  $\leq 8$  weeks; study days 29 to 56)
- Month 3 ( $> 8$  to  $\leq 12$  weeks; study days 57 to 85)
- Month 4 ( $> 12$  to  $\leq 16$  weeks; study days 85 to 112)
- Month 5 ( $> 16$  to  $\leq 20$  weeks; study days 113 to 140)
- Month 6 ( $> 20$  to  $\leq 24$  weeks; study days 141 to 168)
- Month 7 ( $> 24$  to  $\leq 28$  weeks; study days 169 to 196)
- Month 8 ( $> 28$  to  $\leq 32$  weeks; study days 197 to 224)
- Month 9 ( $> 32$  to  $\leq 36$  weeks; study days 225 to 252)
- Month 10 ( $> 36$  to  $\leq 40$  weeks; study days 253 to 280)
- Month 11 ( $> 40$  to  $\leq 44$  weeks; study days 281 to 308)
- Month 12 ( $> 44$  to  $\leq 48$  weeks; study days 309 to 336)
- Month 13 ( $> 48$  to  $\leq 52$  weeks; study days 337 to 364)
- Month 14 ( $> 52$  to  $\leq 56$  weeks; study days 365 to 392).

See Section 7.3 for the definition of study days.

Exposure categories assess the number of months in which a subject exceeded select spray counts in the LTT analysis period (see Section 7.2), where the number of months are not necessarily consecutive. For example, suppose a subject administers 4 sprays in Month 1, 3 sprays in Month 2, 5 sprays in Month 3, 6 sprays in Month 4, and 0 sprays in Month 5. Thus, this

subject is considered to have administered  $\geq 2$  sprays per month for 4 months (i.e., Months 1 through 4),  $\geq 4$  sprays per month for 3 months (i.e., Months 1, 3 and 4), and  $\geq 6$  sprays per month for 1 month (i.e., Month 4).

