## **7 CONVENTIONS**

### **7.1 Derived Dates**

Derived dates for defining analysis periods are defined as follows:

- Study drug date/time: Complete finding date/time corresponding to “yes” response to question about taking study medication and number of sprays  $> 0$  in the eDiary evening report or medication reconciliation form.
- Study drug start date/time: Earliest study drug date/time.
- Study drug end date/time: Latest study drug date/time.
- Study drug last date/time: Study drug end date/time derived only for subjects with non-missing response to the question “Did the subject complete the study?” on the Study Exit Status CRF. Thus, in an interim analysis, all post-baseline data are included for a subject who is still on study. At the last database lock, the study drug last date is equal to the study drug end date.
- LTT start date/time: Earlier of (1) study drug start date/time, and (2) IWRS baseline visit date (i.e., Baseline/Day 1 visit date from the BHV3500\_202 IWRS Visit Report csv file).
- LTT end date/time: Later of (1) latest complete finding date/time in the eDiary on or after the LTT start date/time, and (2) latest complete visit date on or after the LTT start date through the Week 52/Early Termination visit date, and excluding the Follow-up Week 2 visit date, from the Visit Date CRFs.

- LTT last date/time: LTT end date/time derived only for subjects with non-missing response to the question “Did the subject complete the study?” on the Study Exit Status CRF. Thus, in an interim analysis, all LTT data are included for a subject who is still on study. At the last database lock, the LTT last date is equal to the LTT end date.
- OP start date/time: Earliest complete finding date/time in the eDiary before the LTT start date/time.
- OP end date/time: Latest complete finding date/time in the eDiary before the LTT start date/time.
- COVID-19 visit date: (1) Complete visit date, if it exists; (2) otherwise, complete date the visit was planned to occur for a missed visit (see Section 9.1.1).

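### For a subject treated twice in sequence under two identifiers, SAP 7.4 counts the off-study gap and the second observation phase as time in long-term treatment

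*SAP*

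**What the plan says.** SAP 7.4 (Duplicate Subjects) splits the derived dates in two. Start dates come from the first treatment: "Pre-treatment derived dates (i.e., OP start/end dates, LTT start date, study drug start date) are derived using data only from the subject identifier" that corresponds to it. End dates do not: "All other derived dates (i.e., LTT end/last date, study drug end/last date, last contact date) are derived using data from all duplicate subject identifiers". The data are pooled as well: "Protocol deviations, non-study prior medications, exposure, safety, migraine days, and outcomes research endpoints are assessed comprehensively using data from all duplicate subject identifiers".

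SAP 7.1 makes each end date a latest date. For study drug: "Study drug end date/time: Latest study drug date/time". For LTT, it is the later of two dates: the "latest complete finding date/time in the eDiary on or after the LTT start date/time", and the latest visit up to Week 52 or early termination.

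SAP 6.2.6.1 turns these dates into durations. The entries "Time in the LTT period (weeks), derived as" and "Time on zavegepant (weeks), derived as" both use end minus start plus one, divided by 7. Patient-years are "derived by summing (study drug end date – study drug start date + 1)/365.25 across all subjects". From 2 weeks in LTT onward, average sprays per month is 4 times cumulative sprays divided by weeks in LTT. SAP 6.4.6.2 divides treated migraine days by every study day from LTT start to LTT end, whether or not a diary entry exists. SAP 7.2 defines LTT as one continuous interval between its two dates.

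No section of this SAP removes time between enrolments or a second observation phase.

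**The concern.** The start is pinned to the first enrolment and the end floats to the last. When the enrolments are sequential, the span therefore includes two stretches that are not long-term treatment: the interval when the subject is out of the study, and a second pre-treatment observation phase of 28 days, plus or minus 2 (Protocol 4.3.1).

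Two things follow for that subject. Exposure time is too long, and any per-month rate that uses LTT time as its denominator is too low. Both feed categories that the SAP uses to define subgroups or restricted tables:

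- at least 51 weeks in LTT, the stand-in for 12 months, which also restricts tables in 6.2.6.1 and 6.4.6.2
- fewer than 6, or 6 or more, sprays per month (4.3)
- fewer than 2, or 2 or more, treated migraine days per month (4.3)

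The SAP expects that duplicates may occur, since it gives them a section and a deviation category (9.2). The rule should give a sensible answer when one does.

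**Working it through.** The plan gives no figure of its own for duplicate subjects, so there is none to reproduce. The sample-size bound, 1 − 0.05^(1/600) = 0.00498, is not affected.

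**Inputs.** The date rules and formulas are those of SAP 6.2.6.1, 6.4.6.2, 7.1 and 7.4. The observation phase is 28 days (26 to 30). The durations and dosing rates below are assumptions, because the documents give none. The first observation phase, first LTT and gap in the example total 28 + 56 + 28 = 112 days, which fits the planned recruitment period of about 5 months (Protocol 5.1).

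**Formula.** Let L1 and L2 be the two LTT durations, G the gap and O the second observation phase.

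- Time in LTT under the SAP: L1 + G + O + L2
- Time actually in LTT: L1 + L2
- Relative excess: f = (G + O)/(L1 + L2)
- Time is overstated by f. A per-month rate is understated by f/(1 + f).

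**Example: L1 = 56, G = 28, O = 28, L2 = 168.**

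| Quantity | As written | Summed per identifier |
|---|---|---|
| Days in LTT | 56 + 28 + 28 + 168 = 280 | 56 + 168 = 224 |
| Weeks in LTT | 40 | 32 |
| Sprays per month (48 sprays, i.e. 6 per 28 days over 224 days) | 4 × 48/40 = 4.8 | 4 × 48/32 = 6.0 |
| Treated migraine days per month (16 treated days assumed) | 28 × 16/280 = 1.6 | 28 × 16/224 = 2.0 |

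Here f = 56/224 = 25%, and the rates fall by 0.25/1.25 = 20%. At that dilution, true rates from 6 to below 7.5 sprays per month drop under the cut of 6 (7.5 × 0.8 = 6). True rates from 2 to below 2.5 treated days drop under the cut of 2 (2.5 × 0.8 = 2).

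**The 51-week category.** Keep L1, G and O and set L2 = 245. The SAP span is 357 days = 51.0 weeks, so the subject counts as a 12-month exposure. Time actually in LTT is 301 days = 43.0 weeks.

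**Range over other assumed durations (6 sprays per 28 days on treatment).**

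| L1 + G + O + L2 (days) | Weeks, as written vs summed | Excess | Sprays per month, as written vs summed |
|---|---|---|---|
| 84 + 0 + 28 + 84 | 28.0 vs 24.0 | +16.7% | 5.14 vs 6.00 |
| 84 + 60 + 28 + 84 | 36.6 vs 24.0 | +52.4% | 3.94 vs 6.00 |
| 84 + 60 + 28 + 364 | 76.6 vs 64.0 | +19.6% | 5.01 vs 6.00 |
| 56 + 28 + 28 + 364 | 68.0 vs 60.0 | +13.3% | 5.29 vs 6.00 |
| 28 + 90 + 28 + 28 | 24.9 vs 8.0 | +210.7% | 1.93 vs 6.00 |

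**Trial totals.** Assume 1 to 6 such subjects, 28 to 150 excess days each, and 300 to 600 patient-years in all. The excess runs from 1 × 28/365.25/600 = 0.01% to 6 × 150/365.25/300 = 0.8%.

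**The case against.** The strongest reply is that dosing is as needed, so time on zavegepant includes drug-free days for everyone. Protocol 5.4 and 7.2.2 allow dosing to stop and restart, and the SAP subtracts none of that either. On this view, 7.4 merely applies the same single clock. That is fair as a description of the first-to-last-dose measure, but it does not reach this case. A subject on a dosing break is still in LTT. A subject who has left the study, or is in a second screening phase, is not.

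The second reply is that there may be no such subject. Rescreening and re-enrolment are barred (Protocol 4.3.1, 5.3 and 7.2.1), no count is given, and duplicates are tabulated and listed as deviations (SAP 6.2.4.1 and 9.2). This stands as a limit on importance. It does not make the derivation right for a subject who does occur.

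The third concerns migraine days. A reader might infer that diary days from the second observation phase must be removed from the LTT migraine-day analyses. The documents do not support that as a correction. SAP 3.2 assigns those analyses a treatment policy strategy, under which all observed values count, and 6.4.6.1 uses only days with data, so an empty gap already drops out.

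A reader might go further in other ways that the documents do not bear out:

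- **At least 28 days are always added.** The phase can last 26 days, and a second screening could begin before the first LTT ends.
- **No study drug is on hand in the second observation phase.** Protocol 7.4 and SAP 6.2.6.2 both foresee unreturned kits.
- **Sprays after study day 392 are lost.** This needs a span above 392 days, and it touches only the by-month tables. Cumulative and average exposure still include those sprays.

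**Conclusion.** The point holds for exposure time and the rates built on it, when the enrolments are sequential. The excess in LTT time is exactly the gap plus the second observation phase: 13% to 211% of the subject's own treatment time across the assumed cases, and 25% in the worked example. If the enrolments overlap, the excess may be nil.

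The 25% should not be carried over to time on zavegepant or patient-years. Those run from first to last dose, so the gap and second observation phase count only where they fall between those doses, and the base is different.

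This is a minor point. The number of affected subjects is unknown and probably small, the effect on total patient-years is below 1% under the stated assumptions, and the sample-size statement is unchanged. What can go wrong is the classification of individual subjects, mainly those whose true values lie near a cut.

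**What to change.** In SAP 7.4, state that for duplicate subjects the following are derived within each identifier by the 7.1 and 6.2.6.1 rules and then summed, with overlapping dates counted once:

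- time in LTT
- time on zavegepant
- patient-years
- the overall LTT denominators for average sprays per month and treated migraine days per month

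Study days, months and visit windows can stay anchored to the first LTT start. A footnote should say that by-month displays for these subjects run on that calendar and so will not match the summed durations. If wanted, one sensitivity table can show migraine days per month without diary days from a second observation phase; the main analysis need not change.

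The cost is a few sentences in 7.4, the footnote, and special-case code for however many such subjects exist. No new data are needed.

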## 8 CONTENT OF REPORTS

An interim CSR is produced to support the intranasal zavegepant new drug application submission. All TLFs described in this SAP are produced for the interim CSR, except those for the migraine analysis set, exploratory endpoint of migraine days per month, and the subgroup of total treated migraine days per month in the overall LTT (see Sections 4.1, 4.3, and 6.4.6).

The final CSR is produced after the final data base lock, which occurs after the last subject reaches Follow-up Week 2. All TLFs described in this SAP are produced for the final CSR.

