5.1 Number of Subjects

Up to approximately 800 subjects will be screened and up to approximately 600 subjects will treat migraines with study drug in this study. It is anticipated that enrollment will occur at approximately 65 sites in the United States over a period of approximately 5 months.

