### 1.2 Schedule of Analyses

During the course of this study, safety and exposure data are monitored on an ongoing basis. Interim analyses may be conducted after an interim database lock that is prior to last patient last visit. The CSR is produced after the last patient last visit and final database lock. All analyses described in this SAP are performed after the final database lock.

[figure not shown]

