	For the ideation subscale, behavior subscale, and total scores: 
 
• Worst (highest) score on-treatment and follow-up
 
• Change from baseline to worst score on-treatment and follow-up
 
• Number and percentage of subjects in each of 5 worst change from baseline score categories (< -1, -1, no change, 1, > 1) on-treatment and follow-up
 

Safety Endpoint	
Summary	Summary statistics and frequency for the safety analysis set with S-STS data
Intercurrent Events	Study drug discontinuation: while-on-treatment strategy
Objective	Frequency of nasal edema and inflammation from nasal inspection
Safety Endpoint	Number and percentage of subjects with local irritation AEs
Summary	Frequency for the safety analysis set
Intercurrent Events	Study drug discontinuation: while-on-treatment strategy
Objective	Reduction from the OP in the number of migraine days per month by intensity
Safety Endpoint	Values and changes from OP in the number of migraine days per month during LTT (1) over time by month and (2) overall, by migraine intensity (total; moderate or severe)
Summary	Summary statistics for values and changes from OP over time for the migraine analysis set
Intercurrent Events	Study drug discontinuation: treatment policy strategy
Objective	MSQ domain scores and changes from baseline
Outcomes Research Endpoint	Values and changes from baseline in the MSQ score over time for each dimension
Summary	Summary statistics for values and changes from baseline over time for each dimension for the safety analysis set
Intercurrent Events	Study drug discontinuation: treatment policy strategy
Objective	PoM
Outcomes Research Endpoint	Number and percentage of subjects in each of 5 preference categories (much better to much worse) of study medication relative to previous migraine medications
Summary	Frequency for the safety analysis set with PoM data
Intercurrent Events	Study drug discontinuation: treatment policy strategy
Objective	SM
Outcomes Research Endpoint	Number and percentage of subjects in each of 7 satisfaction categories (completely satisfied to completely dissatisfied) of study medication
Summary	Frequency for the safety analysis set with SM data
Intercurrent Events	Study drug discontinuation: treatment policy strategy

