## 6.5 Outcomes Research

Outcomes research questionnaires and rating scales are MSQ, MIDAS, CGI-c, PoM, and SM. Outcomes research endpoints are assessed for the safety analysis set.

Measurements are first slotted into the pre-LTT, LTT and follow-up analysis periods, and then slotted into analysis visits. If a subject has multiple values in an analysis visit window, then the non-missing value assessed closest to the target date for the visit is used; in the case of a tie, the last value assessed and entered is used. See Sections 6.2.4, 7.2, and 7.3 for definitions of baseline, analysis periods, and analysis visit windows, respectively.

Parameters are summarized at baseline, each scheduled visit, and end of study (EOS), as applicable. EOS is defined as the last non-missing post-baseline value assessed and entered in the study.

By-subject listings of outcomes research questionnaires and rating scales (i.e., MSQ; MIDAS; CGI-c; PoM, and SM) are provided for the enrolled analysis set. All listings except PoM and SM display COVID-19 visit impact code for visits impacted by COVID-19 (see Section 9.1.5.2).

Refer to the Zavegeptan Core SAP for detailed descriptions of these questionnaires and rating scales and listing contents.

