#### **6.5.2 PoM**

The PoM is a 5-point rating scale that measures the patient's preference of study medication to previous medications to treat migraine pain. The PoM is evaluated with the eDiary at early termination and Week 52.

The number and percentage of subjects in each category are tabulated at Week 52 and EOS, including 2-sided exact Clopper-Pearson 95% CIs for each percentage. Refer to the Zavegeptan Core SAP for categories.

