#### **6.5.3 SM**

The SM is a 7-point rating scale that captures the subjects' perception of whether they are satisfied with their headache medication. The SM is evaluated with the eDiary at early termination and Week 52.

The number and percentage of subjects in each category are tabulated at Week 52 and EOS, including 2-sided exact Clopper-Pearson 95% CIs for each percentage. Refer to the Zavegeptan Core SAP for categories.

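### The interim CSR would report pooled EOS percentages for PoM and SM that leave out every subject still on treatment and so over-represent early stoppers

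*SAP*

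**What the plan says.** **Collection.** On PoM, SAP 6.5.2 says: "The PoM is evaluated with the eDiary at early termination and Week 52". SAP 6.5.3 says the same of SM: "The SM is evaluated with the eDiary at early termination and Week 52". Protocol Table 1 and Section 4.3.5 agree. Neither scale is scheduled earlier in treatment.

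**Summary.** For PoM, "The number and percentage of subjects in each category are tabulated at Week 52 and EOS", with exact 95% confidence intervals; SM is handled the same way. Under SAP 6.5, "EOS is defined as the last non-missing post-baseline value assessed and entered in the study". The denominator in SAP Table 2 is "Frequency for the safety analysis set with PoM data", with a matching entry for SM. SAP 6.1.3 rules out imputation.

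**Interim report.** SAP Section 8 provides for an interim CSR for the new drug application: "All TLFs described in this SAP are produced for the interim CSR, except those for the migraine analysis set". The sentence continues with the migraine-days endpoint and the treated-migraine-day subgroup. PoM and SM are not on the list.

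**Timing.** SAP 1.2 says: "Interim analyses may be conducted after an interim database lock that is prior to last patient last visit". It gives no date, subject count or exposure trigger. The same section also says that all of the SAP's analyses follow the final lock, which does not fit Section 8.

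**The concern.** At an interim lock, a subject who is doing well and still on treatment has no PoM or SM value and drops out of the denominator. A subject who has stopped can already have one, because Protocol 6.6 asks discontinuing subjects to complete the End of Treatment procedures. Membership of the interim EOS column therefore depends on having left treatment.

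That selection is unlikely to be neutral. Protocol 6.6 lists lack of efficacy and adverse events among the reasons for stopping, and both plausibly bear on preference and satisfaction. It also sits badly with the stated estimand. SAP 3.2 and Table 2 apply a treatment policy strategy to these endpoints, under which discontinuation should make no difference to which values are used. At interim it decides who is counted.

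MSQ, MIDAS and CGI-c do not share the problem to this degree. They are scheduled at Weeks 12, 24 and 36 as well, so an ongoing subject can contribute an EOS value.

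At stake is a pooled percentage with a confidence interval, in a submission document, that does not describe the treated population and will later shift for a purely mechanical reason.

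**Working it through.** The plan gives no figure for this point. Its only sample-size figure, the 0.005 bound for zero events in 600 subjects, reproduces (1 - 0.05^(1/600) = 0.00498) but plays no part here.

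**Inputs from the documents**
- 600 treated subjects (SAP Section 5; Protocol 5.1 says approximately).
- Entry over about 5 months: "approximately 65 sites in the United States over a period of approximately 5 months" (Protocol 5.1).
- Treatment for up to 52 weeks (Protocol 7.2.2), i.e. 364/30.4375 = 11.96 months.

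**Assumptions, because the documents are silent**
- Lock month m, counted from the first baseline visit, varied from 11 to 16.
- Dropout d by Week 52 of 20%, 30% or 40%, at a constant hazard.
- Uniform entry, and a PoM/SM value from every stopper and every completer.

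**Formulas.** A subject entering at time e (0 to 5 months) has potential follow-up a = m - e.
- Hazard: h = -ln(1 - d)/11.96.
- Early stoppers by the lock: 600 x mean of [1 - exp(-h x min(a, 11.96))].
- Completers by the lock: 600 x P(a >= 11.96) x (1 - d).
- Early-stopper share of EOS = stoppers/(stoppers + completers).

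**Worked case, m = 13, d = 30%.**
- h = 0.357/11.96 = 0.0298 per month.
- The fraction able to have reached Week 52 is (13 - 11.96)/5 = 0.208, so 79% cannot have done so.
- Completers: 600 x 0.208 x 0.7 = 87.
- Stoppers: 600 x 0.208 x 0.3 = 37 from those with full follow-up. The others have 8 to 11.96 months of follow-up and a mean stopping probability of 0.257, which gives 600 x 0.792 x 0.257 = 122. The total is about 160.
- Share: 160/(160 + 87) = 65%.

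**Early-stopper share of EOS values**

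| Lock (months from first baseline) | d = 20% | d = 30% | d = 40% |
|---|---|---|---|
| 11 | 100% | 100% | 100% |
| 13 | 51.4% | 64.6% | 74.1% |
| 14 | 36.4% | 49.6% | 60.6% |
| 15 | 28.5% | 40.7% | 51.7% |
| 16 | 23.5% | 34.5% | 45.1% |
| Full follow-up | 20% | 30% | 40% |

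At every lock before the last subject's Week 52 (month 5 + 11.96, about 17), the share exceeds its final value.

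**If stoppers respond less often.** With 60% response among stoppers (an assumption) and full response among completers, the month-14 shares become 26%, 37% and 48%. The matching final shares are 13%, 20% and 29% (for example 0.6 x 120/(72 + 480) = 13%). The level falls but the excess over the final table remains.

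**Effect on the reported percentage.** The shift equals the excess share times the difference in preference between completers and stoppers. At month 13 with d = 30% the excess is 64.6 - 30 = 34.6 points, so each 10-point difference in preference moves the interim figure by about 3.5 points. The documents give no preference rates, so this cannot be taken further.

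**The case against.** The strongest reply has five parts.

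1. **Lock date.** A reader might infer that the interim percentages come mainly or only from early stoppers. The documents do not support that. Only requires a lock before the first Week 52 visit; mainly requires a fairly early lock or high dropout. At 20% dropout the share is already 36% by month 14. SAP 1.2 would even allow a lock after the last Week 52 visit but before the last follow-up visit about 14 days later (Protocol 4.3.6), when the problem disappears. This stands as a limit on size. It does not remove the defect, because nothing in the SAP requires so late a lock. The SAP also plans for ongoing subjects at interim: a disposition category (6.2.3.3), censoring of time on drug (6.2.6.1) and date rules for subjects still on study (7.1).

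2. **Who responds.** It is tempting to say that every early terminator counts. Protocol 6.6 exempts subjects who withdraw consent for all procedures or lose the ability to consent freely, and subjects lost to follow-up (6.6.1) are out of reach. This stands, and it lowers the shares as shown above.

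3. **The Week 52 column.** It is tabulated separately and holds essentially completers, apart from any termination value in the day 351-378 window of SAP Table 3. The criticism does not extend to that column, and comparing the two columns reveals part of the mixture.

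4. **Visibility.** The denominator is declared, listings are provided and disposition shows who is ongoing. Counting rules and table shells sit in the Core SAP and mock TLF document, which were not available and might add footnotes. So one can say only that this SAP contains no rule for the problem.

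5. **Importance.** PoM and SM are exploratory objectives in a single-arm safety study. No test or decision rests on them. This limits the severity.

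**Conclusion.** The point holds for the pooled EOS summaries of PoM and SM in the interim CSR. Followed as written, the plan excludes all subjects still on treatment and over-represents early stoppers at any lock before all subjects have reached Week 52. The column contains early stoppers alone if the lock precedes the first Week 52 visit.

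Under the stated assumptions the early-stopper share is 100% at month 11 and falls to roughly 24-45% by month 16, against 20-40% at the final analysis. The direction follows from the text. The size does not, since it rests on an unstated lock date, dropout rate and response rate.

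A reader should not conclude that all preference and satisfaction results are compromised, or that the final CSR is affected; the final tables are unchanged. This is a correction worth making before the interim outputs are produced. It is not a threat to the study's primary safety objective.

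**What to change.** In SAP Section 8, extend the existing exceptions with one sentence: *the EOS summaries of PoM and SM are also not produced for the interim CSR.* The Week 52 column can stay.

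If the sponsor wants to keep EOS at interim:
- show early-termination and Week 52 responses separately;
- give the number of subjects still ongoing and the number who left without a response;
- do not present the pooled percentage and its confidence interval as an estimate for the treated population.

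In either case, state the interim data cut-off, and reconcile the SAP 1.2 statement that all analyses follow the final lock with the interim outputs in Section 8.

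The cost is a sentence or two in the SAP and one column fewer in two interim tables, or a few extra rows if the split display is chosen. The downside is that the interim CSR has no pooled preference or satisfaction result.
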